2.5 Statistical Analysis

Implant was considered the unit of analysis. MBLC at the mesial and distal aspect of the implant during 1-year follow-up was considered the primary outcome of this study.

Descriptive statistics, including means and standard deviations, were calculated for mesial, distal, and overall MBLC, keratinized mucosa width changes, and lingual mucosa thickness changes across the test and control groups. The Shapiro-Wilk test was used to assess the normality of the data. When the assumption of normality was violated, non-parametric methods were utilized alongside traditional parametric tests. Specifically, paired samples t-tests were used to compare MBLC and soft tissue changes between the two groups.

Wilcoxon signed-rank tests were conducted where normality assumptions were not met.

Correlation analyses were performed to explore relationships between all measured parameters, including MBLC, keratinized mucosa width changes, and lingual mucosa thickness changes. All statistical tests were two-tailed, with a significance level set at $p \leq 0.05$. Statistical analyses were conducted using R Statistics version 4.3.3 (The R Project for Statistical Computing, Vienna, Austria).

REFERENCES

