The Effects of Disconnection and Reconnection of Definitive Abutments on Peri-implant Bone Levels Changes: A 1-Year Split-Mouth Randomized Controlled Clinical Study

This study has been registered in ClinicalTrial.gov ID. NCT04043286

Document Date: Sep 10th, 2024

Abstract

Background: There is evidence suggesting non-removal of a definitive abutment on an implant from the day of surgery helps to preserve the peri-implant marginal bone levels. However, the limited literatures available still contains contradictory conclusions to this finding.

Objective: The aim of this prospective study was to evaluate the effects of definitive abutment connection at the time of implant placement on peri-implant bone levels and soft tissue changes in posterior maxilla and mandible regions.

Materials and Methods: A total of 38 implants were placed in 17 patients with at least 2 missing posterior teeth in the maxilla or the mandible for this study. Each patient received 2 or 4 implants. A definitive prefabricated abutment (test group) was randomly connected to one implant at implant placement (T0) and left undisturbed throughout the duration of the study. On the other implant, a healing abutment (control group) was connected and subjected to go through three disconnections and reconnections at 3 months (T3), 6 months (T6), and 12 months (T12) after the implant placement. Throughout the study period (1 year), all implants remained unrestored. Marginal bone level changes (MBLC) were assessed using standardized periapical radiographs taken at T0 and T12. Peri-implant soft tissue parameters including the keratinized mucosa width and lingual mucosa thickness were also recorded and evaluated.

Results: At the 1-year follow-up, the test group showed significantly less MBLC compared to the control group. The mean MBLC in the test group was 0.32 ± 0.47 mm, which was significantly lower than the 0.80 ± 0.92 mm observed in the control group ($p=0.009$). The test group also had a smaller reduction in keratinized mucosa width, with a mean reduction of 0.42 ± 0.42 mm compared to 0.90 ± 0.77 mm in the control group ($p=0.049$). Lingual mucosa thickness changes were 0.38 ± 0.26 mm in the test group and 0.71 ± 0.59 mm in the control

group, but this difference did not reach statistical significance ($p=0.053$). However, a significant correlation was identified between changes in keratinized mucosa width and MBLC in the test group ($p=0.02$).

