Conclusion: The results of this study support the hypothesis that connecting a definitive abutment at the time of implant placement results in less MBLC compared to repeated abutment disconnections. Additionally, the test group demonstrated better preservation of peri-implant soft tissue compared to the control group. These findings suggest that the one-abutment-one-time protocol may contribute to improved peri-implant tissue stability.

Keywords: *abutment disconnection-reconnection, one-abutment one-time, definitive abutment, one-time abutment, marginal bone loss*

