2.2 Patient selection

This study was designed as a single-center, prospective, randomized modified split-mouth

clinical trial. It was conducted at the Loma Linda University School of Dentistry (LLUSD) Center for Implant Dentistry, California, United States. The study followed guidelines established by the Loma Linda University Institutional Review Board (IRB No.#5190024) and was approved prior to initiation.

To be included in the study, patients had to meet the following criteria: (i) read, sign, and receive a copy of the informed consent form, including consent for photos; (ii) Male or female with at least 18 years of age with good oral hygiene and good general health; (iii) have a healed site with two or more missing teeth in the maxillary or mandibular posterior region (excluding third molars); (iv) have adequate bone width and height to accommodate at least a 4.3 mm diameter and 8 mm length implant at each site; (v) have at least 8 mm of interocclusal restorative space; and (vi) be willing to participate and attend the planned 1-year follow-up visits before starting the implant restoration procedures.

Patients were excluded if they had the following: (i) history of alcohol or drug dependency, or any medical, physical, or psychological factors that might affect the surgical or prosthodontic procedures and follow-up examinations; (ii) history of radiation therapy to the head and neck region; (iii) history or current habit of smoking; (iv) history or current habit of bruxism; (v) no opposing occluding dentition or prostheses; (vi) need for bone augmentation during implant placement; or (vii) implant insertion torque value <35 Ncm. Each patient received at least two implants in the posterior maxilla or mandible. At implant placement (T0), one implant was randomly selected to receive a definitive prefabricated abutment (test group), which was left undisturbed throughout the study. The other implant received a healing abutment (control group), which underwent three disconnections and reconnections at 3 months (T3), 6 months (T6), and 12 months (T12) after implant surgery. All implants were restored with individual screw-retained crowns after the 1-year study period.

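### Implant-level paired tests take no account of the two patients with four implants; the effect is small, but the keratinized-width result (p=0.049) is too close to the threshold to go unchecked at patient level

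*Combined protocol and SAP*

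**What the plan says.** Section 2.5 sets the unit: "Implant was considered the unit of analysis". It compares marginal bone level change (MBLC) and the soft-tissue changes with paired t-tests, and with Wilcoxon signed-rank tests where normality fails; in its words, "non-parametric methods were utilized alongside traditional parametric tests". It describes no patient-level term, averaging or sensitivity analysis.

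The Abstract (Materials and Methods) gives the counts: "A total of 38 implants were placed in 17 patients" and "Each patient received 2 or 4 implants". Section 2.2 is looser: "Each patient received at least two implants in the posterior maxilla or mandible". It describes allocation for two implants only: "one implant was randomly selected to receive a definitive prefabricated abutment (test group", with the remaining one as control. How four implants in one patient were allocated and paired is not described.

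In the Abstract (Results), keratinized mucosa width has p=0.049 ("The test group also had a smaller reduction in keratinized mucosa width"), lingual thickness p=0.053 and MBLC p=0.009. The Abstract (Conclusion) states that "the test group demonstrated better preservation of peri-implant soft tissue compared to the control group".

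**The concern.** A paired test removes anything that a patient adds equally to the test and control implants. It does not remove correlation between two test-control differences from the same patient. Where one patient supplies two differences and they are positively correlated, the 19-pair test uses too small a standard error.

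What is at stake is the soft-tissue conclusion. Of the two soft-tissue group comparisons reported, only keratinized width reaches significance, by 0.001. A result that close should not depend on an independence assumption that the design does not guarantee.

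**Working it through.** **Inputs.** From the Abstract: 38 implants, 17 patients, two or four each. Keratinized width reduction 0.42 (SD 0.42) against 0.90 (SD 0.77) mm, p=0.049. MBLC 0.32 (SD 0.47) against 0.80 (SD 0.92) mm, p=0.009. Both differences are 0.48 mm. Assumed, because the documents do not say: a 2+2 split in the four-implant patients, no missing data, and one value per implant. The intraclass correlation (ICC) of the pair differences within a patient is not given, so it is shown over a range.

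**Patients with four implants.** With a patients having two implants and b having four, a + b = 17 and 2a + 4b = 38 give b = 2 and a = 15. Pairs: 15 + 2×2 = 19, four of them from two patients.

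**Can the reported p be reproduced?** Not from means and SDs alone, because the test-control correlation r is missing. If p=0.049 is a paired t on 19 pairs, t = 2.111 (18 df), the SE is 0.48/2.111 = 0.227, and the SD of the differences is 0.227×√19 = 0.99. Then r = (0.42² + 0.77² − 0.99²)/(2×0.42×0.77) ≈ −0.33 (−0.43 to −0.24 allowing for rounding). The same step for MBLC gives t = 2.927, an SD of 0.71 and r ≈ +0.64.

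**Size of the unit-of-analysis error.** The variance of the 19-pair mean, relative to independence, is 1 + (4/19)×ICC. Type I error at a nominal 5% was simulated with normal differences, 15 single-pair patients and 2 two-pair patients.

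| ICC | True SE / SE used | Type I error, paired t | Type I error, signed-rank |
|---|---|---|---|
| 0.2 | 1.02 | 5.4% | 5.4% |
| 0.5 | 1.05 | 6.2% | 6.2% |
| 1 | 1.10 | 7.4% | 7.5% |

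The t-test on 17 patient differences stays at about 5.0%, and the signed-rank test at about 4.5%. When the sign of each pair difference was instead randomised independently, as happens if every pair has its own allocation and there is no effect at any site, the 19-pair t-test also stayed at about 5.0% to 5.1% at each of these ICCs.

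**Patient-level results, mean difference held at 0.48 mm.** The variance of the 17-patient mean relative to 19 independent pairs is 19×(16 + ICC)/289. That is 1.052 at ICC 0 (SE ×1.026) and 1.118 at ICC 1 (SE ×1.057). The reference distribution is t with 16 df.

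| Reading | ICC 0 | ICC 0.5 | ICC 1 |
|---|---|---|---|
| Keratinized width, 0.049 is a paired t on 19 pairs | p 0.056 (CI −0.01 to 0.97) | 0.060 (−0.02 to 0.98) | 0.063 (−0.03 to 0.99) |
| Keratinized width, r = 0 | 0.033 (0.04 to 0.92) | 0.036 (0.04 to 0.92) | 0.038 (0.03 to 0.93) |
| MBLC, 0.009 is a paired t on 19 pairs | 0.012 (0.12 to 0.84) | 0.013 (0.12 to 0.84) | 0.014 (0.11 to 0.85) |

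For the r = 0 row, the SD of the differences is √(0.42² + 0.77²) = 0.877, which gives p=0.028 on 19 pairs. At r = +0.25 the figures are 0.015 on 19 pairs and 0.019 to 0.022 at patient level. The patient-level p exceeds 0.05 only if r is below about −0.24, −0.20 or −0.16 at ICC 0, 0.5 and 1. If 0.049 is a signed-rank result, this rescaling does not apply.

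**Allowing the mean to move.** Averaging reweights patients, so the point estimate can shift. In simulated data sets with a 19-pair p near 0.049, the patient-level p exceeded 0.05 in about 60% to 70%, with a 5th to 95th percentile range of roughly 0.02 to 0.14. With a 19-pair p near 0.009, essentially none exceeded 0.05.

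**The case against.** The strongest counter-argument is randomisation. Section 2.2 says that the test implant was chosen at random. If each pair was randomised separately and there is no effect at any site, each difference has an independent random sign, pairs from one patient are uncorrelated, and type I error is not inflated. This stands. Inflation needs either one allocation shared across a patient's pairs or treatment effects that vary by patient. The documents establish neither and exclude neither.

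An ICC of 1 is also only an upper bound. It requires identical differences at two sites, and section 2.4 has keratinized width read with a probe marked in 1.0 mm steps. At ICC 0.2 the standard error is off by 2%. This stands too.

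A reader might infer that correct handling of clustering overturns p=0.049. The figures do not support that. On the paired-t reading, p is already 0.056 at ICC 0, so the crossing comes mostly from having 17 units and 16 df. That reading also needs a negative test-control correlation, while MBLC implies a positive one; with r at zero or above, the result stays below 0.05.

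Finally, this is a secondary outcome and only two patients are involved. That limits the importance of the point, but it does not supply the missing patient-level check.

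**Conclusion.** The point holds as a small unit-of-analysis error. The 15 and 2 split follows from the Abstract, and section 2.5 makes no provision for it. Under a 2+2 split and positively correlated differences, the true standard error is 2% to 10% above the one used, and type I error is about 5.4% to 7.5% at ICC 0.2 to 1. Under independent randomisation of each pair with no effect at any site, there is no inflation.

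The primary MBLC result is not threatened if 0.009 is a paired t on one value per implant. That condition matters: section 2.5 names mesial and distal MBLC as primary without defining the overall value, and entering the two sites as separate observations would increase the clustering.

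Keratinized width is unverified at patient level and could fall on either side of 0.05. The documents do not show that it is a false positive, nor would a patient-level p above 0.05 prove that clustering produced the reported result.

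**What to change.** For every outcome, add a patient-level analysis. Average sites and implants within arm and form one test-minus-control difference per patient. Test the 17 differences with a paired t (16 df), or a signed-rank test where normality fails, and report the estimate and 95% confidence interval. This needs no pairing rule and works for any split with at least one implant in each arm. Because the results are already known, show it beside the implant-level result and label it as added afterwards. If the keratinized-width interval includes zero, describe the soft-tissue conclusion as sensitive to the unit of analysis.

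It would help the reader if the report also said how implants were allocated and paired in the four-implant patients, and which test gave each p-value.

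The cost is a paragraph in section 2.5 and a short re-run in R on data already held. The standard error is 2.6% (ICC 0) to 5.7% (ICC 1) larger than for 19 independent pairs, with 2 fewer df. Setting 1 + (4/19)×ICC equal to 19×(16 + ICC)/289 gives ICC = 285/795 = 0.36; above that, the patient-level mean is the more precise of the two. The point estimate may move slightly in either direction.

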2. MATERIALS AND METHODS

2.1 Sample size

Power analysis was carried out to determine the sample size. A sample size of 38 implants was needed to achieve 80% power to detect a difference between the null proportion of 0.500 at a significance level of 0.05.

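### Soft-tissue comparisons and correlations are judged at an unadjusted 0.05 with no order or family, so the soft-tissue conclusion rests on one of two tests (p=0.049) that does not survive a two-test correction

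*Combined protocol and SAP*

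**What the plan says.** Section 2.5 identifies one primary outcome: "MBLC at the mesial and distal aspect of the implant during 1-year follow-up was considered the primary outcome of this study". The same section says that "paired samples t-tests were used to compare MBLC and soft tissue changes between the two groups", with Wilcoxon signed-rank tests where normality fails. The soft-tissue changes it lists are keratinized mucosa width and lingual mucosa thickness.

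One decision rule covers everything: "All statistical tests were two-tailed, with a significance level set at" p ≤ 0.05. No outcome other than MBLC is ranked, and no testing order, family or adjustment is given.

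On correlations, section 2.5 says: "Correlation analyses were performed to explore relationships between all measured parameters". Three parameters follow as examples, so the number of pairs is open. Whether the correlations were run by group is not stated.

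The Abstract reports MBLC at p=0.009. For width it reports a smaller loss in the test group, "with a mean reduction of 0.42 ± 0.42 mm compared to 0.90 ± 0.77 mm in the control group", at p=0.049. It reports thickness (0.38 against 0.71 mm, p=0.053) as falling short, and a test-group correlation between width change and MBLC as significant at p=0.02. Its Conclusion states that "the test group demonstrated better preservation of peri-implant soft tissue compared to the control group".

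**The concern.** Two soft-tissue outcomes were compared at the full 0.05 level. One passes by 0.001 and the other misses by 0.003, yet the Conclusion speaks of peri-implant soft tissue as a whole. With no order or family set in advance, either outcome could have carried that sentence. The chance that at least one crosses 0.05 with no true effect is therefore above 5%.

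The correlation has the same weakness in a less defined form: one significant result is reported from a set of unknown size.

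At stake is whether the trial can claim a soft-tissue benefit or only an exploratory signal. The bone-level conclusion is not at stake.

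**Working it through.** **Inputs.** From the Abstract, Results: p = 0.009 (MBLC), 0.049 (width), 0.053 (thickness), 0.02 (correlation, test group); mean width reductions 0.42 and 0.90 mm. From section 2.5: two-sided threshold 0.05 for every test.

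**The plan's own figures.** The p-values are taken as printed. They cannot be recomputed, because the SD of the paired differences is not given and the documents do not say whether the t-test or the Wilcoxon test produced each one. Section 2.1 sizes the trial "at a significance level of 0.05" and makes no allowance for several outcomes. Its 38 implants cannot be reproduced because no alternative proportion is stated, but nothing below depends on that figure.

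**Width effect.** 0.90 − 0.42 = 0.48 mm less reduction in the test group.

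**Unadjusted familywise error, two soft-tissue tests.** If independent: 1 − 0.95² = 9.75%. Whatever the dependence, it cannot exceed 2 × 0.05 = 10%.

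**Two-test corrections on {0.049, 0.053}.**

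| Method | Width | Thickness |
|---|---|---|
| Bonferroni | 2 × 0.049 = 0.098 | 2 × 0.053 = 0.106 |
| Holm | 2 × 0.049 = 0.098 | max(0.098, 0.053) = 0.098 |
| Hochberg | min(0.053, 2 × 0.049) = 0.053 | 0.053 |
| Benjamini-Hochberg | min(2 × 0.049, 0.053) = 0.053 | 0.053 |

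Neither outcome is at or below 0.05 under any of the four. The size of the miss depends on the method; the miss itself does not. Holm is valid under any dependence between the tests.

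**Three-test Holm with MBLC, {0.009, 0.049, 0.053}.** MBLC: 3 × 0.009 = 0.027. Width: max(0.027, 2 × 0.049) = 0.098. Thickness: max(0.098, 0.053) = 0.098. MBLC survives.

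**Correlation, Bonferroni over assumed families.**

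| Assumed family | Tests | Adjusted p |
|---|---|---|
| MBLC with each soft-tissue change, test group | 2 | 2 × 0.02 = 0.04 |
| All pairs of the three named parameters, test group | 3 | 3 × 0.02 = 0.06 |
| Same three pairs, both groups | 6 | 6 × 0.02 = 0.12 |

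The result lies on either side of 0.05 depending on a count that the documents do not give.

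**Fixed sequence.** Under the order MBLC, width, thickness, each at 0.05, MBLC passes (0.009), width passes (0.049) and thickness fails (0.053). Under MBLC, thickness, width, testing stops at thickness and width is never tested. The answer turns on an order that the plan does not state.

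**The case against.** The strongest defence is that section 2.5 sets a per-test level and never claims familywise control. The null hypothesis at the end of the Introduction concerns bone levels only. Many statisticians leave non-primary outcomes unadjusted, and the two-test family used here is a reviewer's construction. All of this stands. It supports leaving such outcomes unadjusted if they are read as exploratory. It does not support a Conclusion that uses them as a positive finding, and the plan does not label the soft-tissue comparisons exploratory.

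The correlations are already described as done to explore relationships. That also stands; what remains is that the 0.05 rule covers them, one is called significant, and the number tested is missing.

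Four stronger readings are tempting, and the documents do not support them:

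- **That the Abstract calls the width result significant.** It attaches that word to MBLC and to the correlation, not to width. Width is treated as meeting the rule, by contrast with thickness and through the Conclusion.
- **That the correlation fails any reasonable correction.** With a family of two it is 0.04. The wording of section 2.5 points to a wider family, but gives no count.
- **That the plaque and bleeding indices add to the multiplicity of the group comparisons.** Section 2.5 plans no between-group test of either index and none is reported. A four-test error rate (1 − 0.95⁴ = 18.5%) would describe tests that the plan does not contain.
- **That the bone result is undermined.** It is not: 0.027 in the three-test Holm.

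**Conclusion.** The point holds for the soft-tissue and correlation claims only. Of the two soft-tissue outcomes, one meets the plan's own unadjusted rule and neither meets it after a two-test correction (0.098 by Holm, 0.053 by the more lenient methods). The general statement about soft-tissue preservation therefore goes further than the analysis supports. The correlation cannot be judged either way until the number tested is known; its adjusted p-value is 0.04 to 0.12 over families of two to six.

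This rests on three assumptions: the printed p-values are correct, width and thickness form one family, and non-primary status follows from MBLC being the only outcome named primary, since the documents do not use the label secondary. The primary comparison as reported in the Abstract is unaffected. The change is worth making because it alters what the trial may conclude and needs no new data.

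**What to change.** 1. In section 2.5, state that MBLC is the sole confirmatory outcome and that the soft-tissue comparisons and correlations are exploratory.
2. In the Abstract, give width as 0.48 mm less reduction in the test group, unadjusted p=0.049, with the Holm p of 0.098 explicitly marked post hoc. Give thickness in the same form (0.71 − 0.38 = 0.33 mm, unadjusted p=0.053, post hoc Holm p=0.098).
3. Report the correlations as estimates with 95% confidence intervals, state how many were examined and in which groups, and drop the word significant.
4. Limit the soft-tissue sentence of the Conclusion to an exploratory signal for keratinized mucosa width.
5. Do not write a testing order or a Holm procedure into section 2.5 as if it had been planned. The document, dated September 2024, already contains the results, so any such rule would be a post hoc choice presented as prespecified.

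The cost is wording, the count of correlations and intervals from data already held. The downside is a weaker soft-tissue claim.
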